ECOG	Eastern Cooperative Oncology Group
eCRF	Electronic case report form
EDC	Electronic data capture
EORTC	European Organisation for Research and Treatment of Cancer
EUDRACT	European Clinical Trials Database
ECI	Event of Clinical interest
FFPE	Formalin Fixed Paraffin Embedded
GCP	Good Clinical Practice
GMC	Genomic Medicine Centres
HIV	Human Immunodeficiency Virus
HRA	Health Research Authority
IB	Investigator Brochure
ICD	International Classification of Disease
ICHTB	Imperial College Healthcare NHS Tissue Bank
ICMJE	International Committee of Medical Journal Editors
IEC	Independent Ethics Committee
IUD	Intrauterine Device
IDMC	Independent Data Monitoring Committee
IEC	Independent Ethics Committee
IMP	Investigational Medicinal Product

INR	International normalized ratio
IRB	Institutional Review Board
ir-RECIST	Immune-related
ITIM	Immunoreceptor tyrosine-based inhibition motif
ITSM	Immunoreceptor tyrosine-based switch motif
IV	Intravenous
JRO	Joint Research Office
LDH	Lactate dehydrogenase
mAb	Monoclonal Antibody
MDT	Multidisciplinary Team
MedDRA	Medical Dictionary for Regulatory Activities
MHRA	Medicines and Healthcare Products Regulatory Agency
MRI	Magnetic resonance imaging
MSI	Microsatellite instability
NCI CTCAE	National Cancer Institute Common Terminology Criteria for Adverse Events
NHSE	National Health Service England
NSAIDs	Non-steroidal anti-inflammatory drugs
OS	Overall Survival
OTC	Over-the-counter
PD	Progressive Disease
PFS	Progression Free Survival
PR	Partial Response
PS	Performance Status
PT	Prothrombin Time
APTT	Activated Partial Thromboplastin Time
QLQ	Quality of Life Quotient
QoL	Quality of Life
Q2W	Every 2 weeks
Q3W	Every 3 weeks
RBC	Red Blood Cell
RECIST	Response Evaluation Criteria in Solid Tumours
SAE	Serious adverse event
SD	Stable disease (RECIST)
SSAR	Suspected Serious Adverse Reaction
SUSAR	Suspected Unexpected Serious Adverse Reaction
TB	Bacillus Tuberculosis
TILs	Tumour-infiltrating lymphocytes
TMG	Trial Management Group
TSC	Trial Steering Committee
ULN	Upper Limit of Normal
WBC	White Blood Cell
WGS	Whole Genome Sequencing

1. Introduction

responds, with a median survival of 8 months for all the treated patients. There is thus a significant unmet need to change the treatment paradigm in CUP.

There has been recent agreement (March 2017) from UK NHSE to prospectively (deep) whole genome sequence 750 genomes from 250 patients within the 100k-genome project. The combination of this and integration with global projects (see below) will allow a more detailed understanding of the biology of CUP, which should apply in a tumour agnostic manner, potentially to all solid cancers that are highly metastatic at presentation. Within the NHS 100k genomes project, there is the ability to link the data to therapeutic interventions including clinical trials.

In addition, ([name]) is a co-applicant in the current Australian Study (SUPER: Solving Unknown Primary cancer; [name], and [name], are PI's for the Australian CUP genome sequencing project APP1048193– SUPER 2013 to 2016 Funding from Cancer Australia)), which have and are developing tools that might better assess this sensitively in a way that is meaningful to patients with one of its co-primary aims being a comprehensive psychosocial analysis of CUP Patients. We are thus working on better QOL tools for CUP patients.

There are no established standards of care, consensus, or known benefits to second or more lines of therapy in CUP. Hence a new standard of care needs to be established which is well tolerated and beneficial. Any objective responses or disease control of any significant duration, seen in second line or further are rare so the simple observation of Pembrolizumab (as the test drug here) demonstrating any clinical benefit, where there are no other known treatment options would be an important step in further investigating this strategy in the first line setting.

Initially conceived as a two-cohort study, recruitment had proved challenging for cohort 2 (due to COVID issues). A decision was made in January 2021 for a substantial amendment to lift the recruitment cap in cohort 1 as the minimum effect in > 1 participant had been observed and that, as there was no standard of care treatment worldwide for second-line CUP, there would be major interest in understanding meaningful standard of efficacy in cohort 1, as well as in cohort 2 for immunotherapy strategies.

Since this amendment recruitment continued to be difficult, and a new substantial amendment in January 2022 has formally closed the second cohort, due the effect of ongoing COVID-19 pandemic as well as associated clinical factors.

Following the closure of the second cohort, the first cohort sample size is now expanded to a range of 31-67 patients with recruitment to complete at the end of December 2022. The precise statistical implications of the eventual recruitment total are detailed in full within section 3.

2. Study Objectives and Hypotheses

2.1 Primary Objectives

Objectives:

Overall response rates by immune-related (irRECIST) and RECIST criteria:

Disease Control Rate (DCR), Overall Survival (OS) & Progression Free Survival (PFS).

Hypothesis:

Pembrolizumab has Efficacy in CUP:

- as a second-line treatment in terms of Response which translates into improved PFS and OS.
- and treatment leads to rapid improvement in QOL in high metastatic disease burden.

2.2 Secondary Objectives

Objective:

- Incidence of adverse events up to 8 weeks after the last dose of Pembrolizumab.
- Incidence of adverse events up to 8 weeks after the last dose of Pembrolizumab in Performance Status 2 (PS2) patients.

Hypothesis:

- Pembrolizumab is much better tolerated than conventional chemotherapy in CUP patients and PS2 patients may also benefit.

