## **TRIAL SUMMARY**

Abbreviated Title	CUPem
Clinical Indication	A Phase II, Two-Stage, Trial of Pembrolizumab in Cancer of unknown primary
Trial Type	Single Arm, non-randomised; Two-stage; Hypothesis generating
Type of control	None
Route of administration	IV
Trial Blinding	N/A
Treatment Groups	
The study initially opened with a two-cohort design:
 
(i) First Cohort: One or more lines of prior therapy
 
(ii) Second Cohort: First Line untreated CUP patients
 
A substantial amendment in February 2022 has formally closed the second cohort, due to the significant challenges in recruitment caused by the ongoing COVID-19 pandemic as well as associated clinical factors.

Number of trial subjects	Following the closure of the second cohort, the first cohort sample size has been expanded to 31-67 patients. Recruitment will end once 67 patients have been recruited into cohort 1 or at the end of December 2022, whichever is sooner. The precise statistical implications of the eventual recruitment total are detailed (section 8).
Eligibility Criteria	
The Eligibility Criteria are the same as used in the CUP-ONE trial in the UK, please see below.
 
 
• Histologically confirmation of a diagnosis of CUP, with imaging and all diagnostic investigations confirmed as CUP within a CUP MDT.
 
• ECOG Performance Status 0-2
 
• Patients must have disease that is not amenable to potentially curative options such as resection or radical radiotherapy
 
• If patient's disease presentation precludes tumour biopsy (inaccessible or biopsy thought not to be in the patient's best interest), the patient is not study eligible.
 

Estimated recruitment period	2 years
Estimated duration of trial	3.9 years including set up, recruitment, follow up and close down.
Duration of Participation	6-8 months

CUPem	C/37/2017	Imperial College London	V7.0; 08.12.2021
-------	-----------	----------------------------	------------------

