## 1.2 Rationale

### 1.2.1 Rationale for the Study and Selected Subject Population

The pathogenesis of CUP is poorly understood. The clinical presentation of a high and poorly differentiated, rapidly progressive tumour burden, without an obvious primary site, leads to an intriguing hypothesis that early transforming malignant and invasive CUP phenotypes, have preferential ability to metastasize rapidly, rather than grow locally initially as in most cancers. One possible explanation of these CUP phenotypes are 'immuno-evasive' leading to unchecked and rampant early spread. This would make the clinical testing of PD-1 inhibitors compelling given their remarkable success in other aggressive phenotypes to date.

The current standard of care for patients, as recently verified in the CUP-ONE trial is ECX (Epirubicin, Cisplatin and Capecitabine (Xeloda®)) chemotherapy administered intravenously and orally in the UK. Each cycle of ECX takes 21 days (3 weeks). However, this standard varies worldwide with alternatives being Gemcitabine and Cisplatin (or Carboplatin) and in the USA – the common first choice option is Paclitaxel with Carboplatin. However, the majority of patients do not get any treatment due to their diminished performance status at presentation (66% of CUP patients are PS2 or more). Overall, the prognosis for CUP patients remains very poor at a median of 6-9 months with conventional chemotherapy, which is poorly tolerated in the PS2 patients, which form the majority of CUP patients. There is thus an urgent need for newer therapeutic approaches in this high area of unmet need. Additionally, CUP is a paradigm for the heterogeneity seen in many solid tumours, when they become highly metastatic, as therapy resistance occurs and become rapidly lethal. Equivalent to ECX is the newer variation EOX (Epirubicin, Oxaliplatin and Capecitabine (Xeloda®)), where the cisplatin is substituted to Oxaliplatin, which is more convenient, shorter, less emetogenic and requires less intravenous hydration.

CUPem	C/37/2017	Imperial College London	V7.0; 08.12.2021
-------	-----------	----------------------------	------------------

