## 8 STATISTICAL ANALYSES

### 8.1.1 Statistical Analysis Plan

Response rates can be assessed in patients who have completed at least 2 cycles of trial therapy

- Overall response rates by immune-related (irRECIST) & RECIST criteria:
  - Disease Control Rate (DCR), Overall Survival (OS) & Progression Free Survival (PFS).
- Overall response rates by immune-related (irRECIST) & RECIST criteria in a First-line setting
  - DCR, OS & PFS.
- QOL analysis by EORTC-QLQC30.
- Incidence of adverse events up to 8 weeks days after the last dose of Pembrolizumab.
  - incidence of adverse events up to 8 weeks days after the last dose of Pembrolizumab in PS2 patients.
- Exploratory Identification of genomic biomarkers predictive of immune response to Pembrolizumab in CUP patients and correlates of efficacy, toxicity and QOL.
  - Where patients are co-registered and consented to the NHSE 100k genome project – the data from this project will be requested to cross-correlate with this study.

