3.1 Study Design

An open label, non-randomised, single arm, sequential phase (two sequential cohorts) study, evaluating the preliminary efficacy of Pembrolizumab in Cancer of unknown Primary (CUP).

A substantial amendment in January 2022 has formally closed the second cohort, due to the significant challenges in recruitment caused by the ongoing COVID-19 pandemic as well as associated clinical factors.

Cohort 1:

Cohort 1 will enrol a minimum of 31 patients and a maximum of 67 patients, who have had at least one prior line / regimen of chemotherapy (at least 2 cycles) appropriate for CUP and who have not had a RECIST response to first-line chemotherapy, or are progressing after an initial response, or are treatment intolerant to first-line chemotherapy, due to unacceptable toxicity.

Cohort 2:

Cohort 2 is now formally closed. This cohort had sought to enrol patients who are chemo-naïve (first-line setting) for CUP, with a PS 0-2.

Patients will undergo screening procedures during a standard 28-days time window from initiation of the study, under standard GCP and informed consent. Restaging will be performed by computerized tomography using ir-RECIST criteria at 3 months from initiation of systemic treatment and on an 8 weekly basis thereafter until radiological proven disease progression or intolerance or patient choice.

The EORTC QLQ-C30 questionnaire (to assess the quality of life) will be done at baseline after 3 months and then at discontinuation of study treatment.

Correlative translational study samples (blood) and tissue (used for histological confirmation and to document PD-L1 expression) will be collected at baseline, and blood and serum samples monthly (after an informed optional consent and banked for retrospective immune-modulating and other biomarkers for future research and analysis).

Patients will also be separately consented to the NHSE CUP 100K genome project that will be running in the UK by 2018, for deep sequencing of tumor tissue and germline, in centers participating in, or with access to the UK framework for this programme.

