5.2 Secondary Efficacy Endpoints

- The incidence of adverse events up to 8 weeks after the last dose of Pembrolizumab will be noted.
- Incidence of adverse events up to 8 weeks after the last dose of Pembrolizumab in Performance Status 2 (PS2) patients.

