5.10 Exploratory Variables

Exploratory variables include genomic biomarkers predictive of immune response to Pembrolizumab. Genomic sequencing will be done within the 100K-genome project, the data from which can be linked to this and other CUP trials. This is not costed in this application and the analysis will not be included in this statistical analysis plan.

6 Statistical Methodology

The study data will be summarised using standard descriptive methods by cohort and as combined data. Histograms and box-plots will be used to assess the distributional assumptions and to check for possible outliers. Mathematical transformations will be applied, where appropriate, in order to render variables normally distributed. Continuous variables that follow an approximately normal distribution will be summarised using the mean and standard deviation (StDev). Skewed continuous variables will be summarised using the median and inter-quartile range (IQR). Categorical variables (binary, ordered and multinomial) will be presented in terms of frequencies and percentages.

The primary outcome and secondary outcome will be tested using a two-tailed hypothesis test with a 5% significant level.

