6.4 Secondary Efficacy Analysis

Incidence of adverse events up to 8 weeks after the last dose of Pembrolizumab will be measured.

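### The tolerability hypothesis against chemotherapy cannot be tested in this single-arm trial, and the named PS2 adverse-event endpoint is not carried into the SAP's analysis sections or tables

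*SAP*

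**What the plan says.** Protocol 2.2 and SAP 2.2 give the same secondary hypothesis: "Pembrolizumab is much better tolerated than conventional chemotherapy in CUP patients and PS2 patients may also benefit". The objectives above it are adverse-event incidence up to 8 weeks after the last dose, in all patients and in PS2 patients.

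The opening of SAP section 6 says: "The primary outcome and secondary outcome will be tested using a two-tailed hypothesis test with a 5% significant level".

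On design, SAP 3.1 describes "An open label, non-randomised, single arm", and the protocol's Trial Summary gives the trial type as "Single Arm, non-randomised; Two-stage; Hypothesis generating", with no control.

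SAP 5.2 lists the PS2 endpoint: "Incidence of adverse events up to 8 weeks after the last dose of Pembrolizumab in Performance Status 2 (PS2) patients". Protocol 8.1.1 lists it too: "incidence of adverse events up to 8 weeks days after the last dose of Pembrolizumab in PS2 patients". The matching analysis section, SAP 6.4, consists of one sentence: "Incidence of adverse events up to 8 weeks after the last dose of Pembrolizumab will be measured". SAP 6.5 tabulates adverse events and serious adverse events by cohort.

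**The concern.** The hypothesis is a comparison with chemotherapy, and the SAP attaches a 5% two-sided test to the secondary outcome. Adverse-event incidence is the only secondary outcome, so the test sentence must refer to it. Nothing in either document supplies the other side of the comparison.

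Two things are at stake. First, a reader told that the secondary outcome was tested could take a single-arm adverse-event rate as support for the claim of better tolerability. Second, PS2 patients are central to the trial's rationale: protocol 1.2.1 says that 66% of CUP patients are PS2 or more and that conventional chemotherapy "which is poorly tolerated in the PS2 patients". Yet the endpoint written for them has no method and no table.

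**Working it through.** The documents state no sample size, power, null rate or margin for this hypothesis, so there is no figure of the plan's own to reproduce.

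**Step 1. What the test would need.** A one-sample test of an adverse-event proportion compares the observed p̂ among n patients with a fixed null p0, for example z = (p̂ − p0) / √(p0(1 − p0)/n), or its exact binomial equivalent. The trial supplies p̂ and n. For p0 the documents offer:

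- Trial Summary: no control.
- Protocol 1.2.1: a qualitative remark on poor tolerance in PS2 patients, with no rate.
- Protocol 1.1 and SAP section 1, on the CUP-ONE trial: about a third of treated patients responded and median survival was 8 months; no adverse-event rate is given.

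There is therefore no p0 and the test cannot be computed. A p0 chosen after the data are seen would settle the answer. With 22 of 44 patients having an event, the exact 95% interval is 35% to 65% (step 3), so the same data would reject p0 = 70% and not reject p0 = 60%.

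**Step 2. Where the PS2 endpoint goes.**

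| Place | PS2 adverse events? |
|---|---|
| Protocol 2.2 and SAP 2.2, objectives | Named |
| Protocol 8.1.1 | Named, no method |
| SAP 5.2, endpoints | Named |
| SAP 6.4, analysis | Absent |
| SAP 6.5, safety analysis | Absent; split is by cohort |
| SAP Tables 6 to 11 | Absent; split is by cohort |
| SAP Table 15 | ECOG appears only as a by-visit summary |

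SAP 6.3 gives no response, DCR, PFS, OS or quality-of-life analysis by performance status. In the Table 6 and Table 9 shells the percentages are attached to event counts, while the patient columns hold counts only. The proportion of patients with an event is therefore not laid out even overall.

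**Step 3. What a PS2 estimate could show.** Eligibility is PS 0–2 with no PS2 quota, so the PS2 count is an assumption. I take 10% to 66% of N = 31 to 67. The 66% is the documents' figure for the disease (PS2 or more), not for this trial; the 10% is my assumption. The smallest count is 0.10 × 31 ≈ 3 and the largest is 0.66 × 67 ≈ 44. The event rate is assumed to be near 50%.

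Clopper-Pearson limits for x of n: lower = the 2.5% quantile of Beta(x, n − x + 1); upper = the 97.5% quantile of Beta(x + 1, n − x).

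| N | PS2 share | PS2 patients | Events | Exact 95% CI |
|---|---|---|---|---|
| 31 | 10% | 3 | 2 | 9% to 99% |
| 31 | 20% | 6 | 3 | 12% to 88% |
| 31 | 66% | 20 | 10 | 27% to 73% |
| 67 | 66% | 44 | 22 | 35% to 65% |

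Even the most favourable case leaves an interval 30 percentage points wide.

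**The case against.** The best defence is that the working plan is already descriptive. The protocol calls the trial hypothesis generating, the PS2 wording is hedged, and no sample size, decision rule or alpha is assigned to PS2. The test sentence in SAP section 6 is generic; the specific sections speak only of measuring and tabulating, and none instructs a comparison with chemotherapy. The shells also give useful detail by grade, relatedness, seriousness and MedDRA term.

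Much of this stands, and it rules out three stronger readings that a reader might infer:

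- *That no PS2 analysis was planned.* Protocol 8.1.1 and SAP 5.2 both name PS2 adverse-event incidence. What is missing is its method and its table.
- *That PS2 benefit is put forward as a confirmatory subgroup claim.* The trial's label and the hedged wording do not support that.
- *That an informal comparison with chemotherapy would favour pembrolizumab through patient selection.* The documents do not establish a direction. Cohort 1 admits PS 0–2 and patients intolerant of first-line chemotherapy because of toxicity. Chemotherapy recipients were selected too: protocol 1.1 reports that two-thirds of CUP-ONE patients were offered no treatment. The comparison would be confounded, and no more than that can be said.

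The defence does not remove the core problem. A hypothesis-generating label supplies no null value. The generic test sentence explicitly includes the secondary outcome and conflicts with SAP 6.4. An endpoint named in three places but absent from every analysis section and shell is likely to go unreported.

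**Conclusion.** The point holds in two parts. The comparative tolerability hypothesis is untestable by design, because there is no control arm and no external rate or margin; the 5% test has nothing to be applied to. The PS2 adverse-event endpoint is a repairable omission from SAP 6.4, SAP 6.5 and Tables 6 to 11.

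PS2 incidence can be described but not precisely: the exact 95% interval runs from about 9%–99% (2 of 3) to 35%–65% (22 of 44). This range rests on the assumed PS2 share of 10% to 66% and an event rate near 50%.

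This should be corrected, but it affects secondary claims and reporting only. No sample size or stopping decision depends on it. Efficacy by performance status is not required by any stated objective; it becomes relevant only if the remark about PS2 benefit is meant as an efficacy statement.

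**What to change.** 1. In protocol 2.2 and SAP 2.2, replace the hypothesis with an estimation aim: adverse-event incidence overall and in patients with baseline ECOG PS 2, with PS 0–1 shown alongside.
2. In the test sentence of SAP section 6, delete the reference to the secondary outcome.
3. In SAP 6.4 and the AE and SAE summary tables, report the number and percentage of patients with events, with exact 95% confidence intervals, overall and by baseline PS.
4. State that no conclusion of better tolerability than chemotherapy will be drawn, unless a sourced external benchmark is pre-specified.
5. If the remark about PS2 benefit is kept as an efficacy statement, show DCR, PFS and OS by PS descriptively, labelled exploratory and without p-values.

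The collection window should be reconciled at the same time. The endpoint runs to 8 weeks (56 days), but protocol 7.2 collects adverse events only to the Safety Follow-Up visit, which protocol 5.4 places about 30 days after the last dose; only serious events run to 90 days. Confidence intervals do not repair that gap.

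Items 1 to 5 cost some protocol and SAP wording and a few table columns. ECOG status is already collected at screening, so no patient procedure changes. The sponsor gives up a comparative claim that the design cannot support.

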2.3 Exploratory Objectives

Objective:

- Identification of genomic biomarkers predictive of immune response to Pembrolizumab.

Hypothesis:

- CUP patients have identifiable biomarkers predictive for Pembrolizumab efficacy.
- CUP patients have high mutational loads and this correlates with increased efficacy with Pembrolizumab.

- CUP patients have high mutational loads and this correlates with increased efficacy with Pembrolizumab

(Note: Results for the exploratory objective will not be included in the Clinical Study Report (CSR) but will be reported separately according to standard ethical and regulatory guidelines.)

3. Design

3.1 Study Design

An open label, non-randomised, single arm, sequential phase (two sequential cohorts) study, evaluating the preliminary efficacy of Pembrolizumab in Cancer of unknown Primary (CUP).

A substantial amendment in January 2022 has formally closed the second cohort, due to the significant challenges in recruitment caused by the ongoing COVID-19 pandemic as well as associated clinical factors.

Cohort 1:

Cohort 1 will enrol a minimum of 31 patients and a maximum of 67 patients, who have had at least one prior line / regimen of chemotherapy (at least 2 cycles) appropriate for CUP and who have not had a RECIST response to first-line chemotherapy, or are progressing after an initial response, or are treatment intolerant to first-line chemotherapy, due to unacceptable toxicity.

Cohort 2:

Cohort 2 is now formally closed. This cohort had sought to enrol patients who are chemo-naïve (first-line setting) for CUP, with a PS 0-2.

Patients will undergo screening procedures during a standard 28-days time window from initiation of the study, under standard GCP and informed consent. Restaging will be performed by computerized tomography using ir-RECIST criteria at 3 months from initiation of systemic treatment and on an 8 weekly basis thereafter until radiological proven disease progression or intolerance or patient choice.

The EORTC QLQ-C30 questionnaire (to assess the quality of life) will be done at baseline after 3 months and then at discontinuation of study treatment.

Correlative translational study samples (blood) and tissue (used for histological confirmation and to document PD-L1 expression) will be collected at baseline, and blood and serum samples monthly (after an informed optional consent and banked for retrospective immune-modulating and other biomarkers for future research and analysis).

Patients will also be separately consented to the NHSE CUP 100K genome project that will be running in the UK by 2018, for deep sequencing of tumor tissue and germline, in centers participating in, or with access to the UK framework for this programme.

